7.2 Setting

7.2.1 Population

The present study will include consecutive HFrEF patients treated by office-based cardiologists or selected primary care physicians (recognized as HF specialists) across Europe.

The study will include overall 6000 patients on SoC and 6000 patients on sacubitril/valsartan.

Considering that the different local regulations on patient management and reimbursement can significantly impact clinical practice, patient numbers will be allocated to bigger countries and/or clusters of smaller countries with similar healthcare systems in order to ensure the representativeness of the sample.

Enrollment will start in each country when sacubitril/valsartan is available for clinical use. Assuming that the penetration of sacubitril/valsartan into clinical practice will be slow immediately after launch, the enrollment of sacubitril/valsartan patients will take a significantly longer time than including SoC patients. At each country level the enrollment of sacubitril/valsartan patients will be continuous, while the enrollment of SoC patients will be divided into two phases, where approximately one half is immediately enrolled at the start of the study and the other half is enrolled during the last part of enrollment into the sacubitril/valsartan group (see Figure 7-1). By structuring the enrollment of SoC patients in this two-wave pattern, the possibility is created to compare the baseline demographic and medical characteristics of patients that drive the choice of physicians toward individualized SoC or sacubitril/valsartan (main objective) and see if their approach changes over time, after the launch of sacubitril/valsartan.

LCZ696 launch in Country A ~ 50 % ~ 50 % SoC SoC 100% LCZ696 Phase 2 Phase 1 Phase 3 12 months В ~ 50 % ~ 50 % LCZ696 launch in Country SoC SoC 100% LCZ696 Phase 1 Phase 2 Phase 3 12 months S ~50 % ~ 50 % LCZ696 launch in Country SoC 100% LCZ696 Phase 1 Phase 2 Phase 3

Figure 7-1 Enrollment schedules (examples) on single country level

Overall enrollment: 24 months

Enrollment schedule for each country will depend on enrollment numbers in SoC and sacubitril/valsartan groups and thus might need to be divided into phases, where SoC enrollment is split up in two phases, while LCZ696 enrollment is continuous (examples A-C). SoC = standard of care, LCZ696 = sacubitril/valsartan

12 months

Note: The decision to treat a patient with individualized currently available therapies (SoC) or to start sacubitril/valsartan is to be taken by each investigator according to his/her clinical judgment and independently form participation in this study. Only after that decision is taken, the patient will be enrolled, in order to respect and describe real world clinical practice.

Every effort will be made to reduce selection bias by enrolling patients on a consecutive basis. This also means that patients, who already have been initiated on sacubitril/valsartan treatment after the drug has become commercially available can be included into the study, if they satisfy all inclusion and exclusion criteria and the investigator has the sufficient baseline information (see Section 7.3) on file for these patients.

Follow-up for all patients will last up to 12 months after the baseline visit. The follow-up will consist of 2 visits closest to 6 months and 12 months after the baseline visit, respectively (recommended visit window of \pm 2 months). No exact date for the second and final visits will be enforced, to avoid interference with the real life routine care. In case intermediate visit (6 month) will not take place, this will be recorded and described as part of real world practice.

At any time during the study, the investigator is free to adapt or change the patient's CHF treatment as per his/her clinical judgement at any time – the reasons for switching treatments as well as specific details of the new CHF treatment will be documented. The duration of the patient's follow-up is not altered by the switching of therapy, i.e. the individual follow-up duration is only dependent on the time point of the enrollment.

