With HF mortality remaining at unacceptably high rates, novel treatment approaches are urgently needed. Sacubitril/valsartan (also called LCZ696) constitutes the first of a new class of drugs – Angiotensin Receptor-Neprilysin Inhibitors, ARNIs – designed to replace the current role of ACE inhibitors or Angiotensin receptor blockers (ARBs) in the management of HF. In a recent phase III trial (PARADIGM-HF), sacubitril/valsartan at a target dose of 200 mg BID reduced cardiovascular mortality by 20% compared to a evidence-based dose of the ACE inhibitor enalapril (10 mg BID) (McMurray, Packer et al. 2014). While PARADIGM-HF established a superior efficacy of sacubitril/valsartan with a safety profile comparable to that of enalapril, it appears extremely important to gather additional data on its use and effectiveness in a real life setting, such as which patients are started on sacubitril/valsartan; the pattern of administration of the drug at start and the proportion of patients able to tolerate the drug at different doses; the impact on healthcare resource utilization; quality of life (QoL); main efficacy and safety events in a real-life setting with a more diverse set of patients,

The above mentioned questions will be addressed within the present prospective non-interventional study (NIS). ARIADNE will enroll and describe 12.000 symptomatic CHF patients with reduced left ventricular ejection fraction (HFrEF) treated by specialists in an office-based setting across European countries: 6000 patients treated with current standard of care (SoC) and 6000 patients on sacubitril/valsartan. Enrollment in both cohorts will start in each single country when sacubitril/valsartan is available for use in clinical practice.

Research question and objectives

The main objectives of the present NIS are to provide an European picture of (i) the demographic and clinical features of HFrEF patients managed in the outpatient sector and the diagnostic and pharmacological interventions they receive and (ii) the demographic and clinical features of patients for whom the treating physician decided to start sacubitril/valsartan, the pattern of administration of this drug, the diagnostic and therapeutic interventions these patients receive and the safety and tolerability profile of this drug in real life.

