Before the modern era of treatment in the 1990s', 60-70% of patients died within 5 years of diagnosis (McMurray, Adamopoulos et al. 2012). Mortality has since then decreased significantly, but has not levelled off anymore since the late 1990s, with a current 3-year mortality remaining above 25% for HF patients above 55 years of age (Barasa, Schaufelberger et al. 2014) and 50% at 5 years (Friedrich and Bohm 2007, McMurray, Adamopoulos et al. 2012). In spite of the introduction of new diagnostic procedures (echocardiography, NT-proBNP), of drug therapies with a proven mortality benefit and of devices such as cardiac resynchronization therapy (CRT) and implantable cardioverter defibrillator (ICD), patients with CHF still face a severe prognosis.

Several explanations for this persistently dismal prognosis are discussed:

- Randomized controlled drug trials in CHF, while showing morbidity and mortality benefits of drug therapies, have excluded important categories of patients such as the elderly with comorbidities, those with significant renal dysfunction or low blood pressure.
- Patients with comorbidities constitute a large proportion of those seen in daily practice by practitioners in the out-patient setting. A Dutch study calculated that 78% of patients older than 80 years seen by primary care physicians are multi-morbid (van den Akker, Buntinx et al. 1998). This is true for HF patients as well. The elderly and comorbid CHF patients are being managed most often by the general practitioners, who are not experts in HF management.
- Heart failure is a heterogeneous disorder, and its diagnosis can be challenging. Heart failure with preserved left ventricular ejection fraction (HFpEF) in particular constitutes a clinical challenge and requires exclusion of other diagnoses before it can be established. Primary care physicians, are less familiar with the necessary distinction between HFpEF and HFrEF making them uncertain about the proper handling of CHF overall.
- Poor drug compliance by HF patients might play a prognostic role as well, through undertreatment, suggesting that new therapeutic options may have neglected quality of life concerns (e.g. drug or device side effects) (Lainscak, Cleland et al. 2007).

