The present non-interventional study will aim to provide a Europe-wide picture of (i) the demographic and clinical features of HFrEF patients managed in the outpatient sector and the diagnostic and pharmacologic intervention they receive; (ii) the demographic and clinical features of patients the treating physician decided to start sacubitril/valsartan, the pattern of administration of this drug, the diagnostic and therapeutic intervention these patients receive and the safety and tolerability profile of this drug in real life.

Main objectives:

- To describe the profile of patients initiated on sacubitril/valsartan and patients continued on SoC in the outpatient sector in terms of demographics, medical history, HF status, comorbidity burden
- To describe the profile of sacubitril/valsartan patients not reaching and maintaining the target dose of 200 mg twice daily in terms of demographics, medical history, HF status, comorbidity burden as compared with patients reaching the target dose

Additional objectives:

- To describe the overall HFrEF population managed in the outpatient sector in Europe in terms of demographics, medical history, comorbidity burden and previous cardiovascular (CV) events rate
- To describe HF-treatment (pharmacological and non-pharmacological) in the outpatient sector in Europe and in individual countries/country clusters
- To describe the starting dose, titration and maintenance dose of sacubitril/valsartan in patients with different anamnestic and demographic characteristics
- To assess the rates of major HF related outcomes (death, hospitalizations, major CV events)
- To describe Healthcare Resource Utilization in HFrEF patients managed in the European routine practice
- To describe safety and tolerability features of sacubitril/valsartan in real-world HF patients
- To describe the quality of life (QoL) during follow-up (only in those sites where the EQ-5D and/or KCCQ QoL questionnaires are part of routine CHF management)
- To describe the levels of BNP / NT-proBNP (only if these measurements are available or at sites where these measurements are performed within the routine CHF management)

7 Research methods

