7.2.3 Exclusion criteria

- 1. Concomitant or planned participation in any interventional clinical trial
- 2. Patients who are receiving ongoing treatment with sacubitril/valsartan that has been started prior to market launch in their respective country, e.g. within a clinical trial or early access program.
- 3. Patient still within the safety follow up phase of any previous interventional or non-interventional trial using sacubitril/valsartan (LCZ696), independently whether they received sacubitril/valsartan or the comparator.
- 4. Acute decompensated HF requiring hospitalization at the moment of enrollment.
- 5. Existing contraindications according to approved product information

No additional restrictions for inclusion or exclusion are provided in order to ensure that the patients enrolled are as close as possible to (i.e. representative of) the real population of CHF patients with reduced LVEF managed in the office-based setting.

Page 21

7.3 **Variables**

- Demographics (age, gender, living at home or institution, relationship status, education)
- Medical history and comorbidity burden (with focus on duration of HF, etiology of CHF, last hospitalization for HF, cardiovascular conditions, specific comorbidities such as diabetes, renal insufficiency, COPD, anemia, obesity, cancer)
- Clinical Events (both retrospectively over the past 12 months and prospectively, as applicable):
 - Death (CV related and non-CV related, only prospectively)
 - Hospitalizations (defined as at least one overnight staying): number, elective or not, reason for hospitalization (CV related, HF related, non CV related)
 - **Myocardial Infarction**
 - Stroke
- Number of visits (other than hospitalization) by provider and primary reason during follow-up:
 - Emergency room/department
 - Outpatients office visits (general practitioner; cardiologist; internist; other specialist)
 - Cardiology (day) clinic
 - Device clinic
 - Nurse services/ day clinic
 - Rehabilitation facilities
- Diagnostic and therapeutic procedures utilized during follow-up (Results will be collected only as available for blood potassium, blood creatinine, BNP, NT-proBNP and for echocardiographic EF. In all other cases, the eCRF will only capture if the procedure has been performed and its primary reason)
 - Echocardiogram (LVEF in % if available)
 - ECG / stress ECG
 - Chest X ray
 - Pulmonary function tests
 - Computed Tomography of the Heart
 - Cardiac Magnetic Resonance Imaging
 - Cardiac catheterization

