7.7 Data analysis

All analyses will be performed by the designated CRO.

Only descriptive data analyses will be carried out, supported by calculation of confidence intervals. No statistical testing will be performed.

The two patient populations will be considered and analyzed separately. The SoC group will allow the representative picture of current CHF management as mentioned above. The Sacubitril/valsartan stratum will provide early insight into the adoption of this new therapy, once it will be available in the different countries. Therefore also strata for patients switching between SoC and Sacubitril valsartan will be analyzed upon adequate subgrouping.

The two studied groups, SoC and sacubitril/valsartan, are expected to differ significantly depending on the progressive adoption of sacubitril/valsartan by the prescribers – this will be assessed by stratified analysis according to the above described enrollment phases. In addition, besides baseline characteristics of the patients leading to the physicians' decision to prescribe sacubitril/valsartan or continue SoC, no inferences can be made from the comparison of the characteristics of both populations. For the same reason, no comparison of data obtained during the follow-up phase between the treatment groups is planned. Similarly, no safety comparisons will be performed between SoC (where in most cases an established therapy is merely continued) and sacubitril/valsartan (where a new therapy is prescribed).

Analyses will be performed for the total sample and stratified by demographic, anamnestic and medical factors (e.g. sex, duration of HF, severity of HF, previous HF-treatment) using an adequate grouping. Similarly, data will be also analyzed stratified according to enrollment phase (phase 1 and phase 3) and treatment group (e.g. SoC, valsartan/sacubitril, switching between both groups).

The Statistical Analysis Plan will be created as a separate document prior to data base lock for any analysis (e.g. interim analyses, final analysis). This document will contain sufficient details to enable the generation of the analysis of the NIS and specifies:

- the statistical database underlying the evaluation, including all adjustments, implementations and the calculation of derived variables,
- the detailed establishment of the analyzed population(s), and
- the statistical procedures.

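### The protocol claims the overall outpatient HFrEF population but recruits only through cardiologists and HF-specialist primary care physicians, and does not list this as a limitation

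*Protocol*

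**What the plan says.** **The frame.** Section 7.2.1 enrols patients of office-based cardiologists and of "selected primary care physicians (recognized as HF specialists". The abstract (Section 2) agrees, describing patients "treated by specialists in an office-based setting across European countries".

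**The claims.** One additional objective in Section 6 is "To describe the overall HFrEF population managed in the outpatient sector in Europe". Section 7.7 says: "The SoC group will allow the representative picture of current CHF management". The rationale in Section 2 promises a representative picture of CHF management in Europe, and Section 7.9 speaks of a representative sample of CHF patients from the outpatient sector.

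**Who is outside the frame.** Section 5 states: "The elderly and comorbid CHF patients are being managed most often by the general practitioners, who are not experts in HF management". The same bullet says that comorbid patients make up a large part of everyday outpatient practice.

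**Precision.** Section 7.5 gives, for 6000 patients per group, a 95% confidence interval of at most ±1.3 percentage points for qualitative parameters. For 3000 patients it gives ±1.8 points.

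**The concern.** The population named in the objectives is wider than the population that can be sampled. A patient managed only by a non-specialist general practitioner cannot enter the study, yet belongs to the outpatient sector that the protocol says it will describe.

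On the protocol's own account this group is not a random remainder, since it is where older and comorbid CHF patients tend to be. Age and comorbidity burden are among the variables that the first main objective reports, and that objective is itself stated for the outpatient sector. If the results are read as a picture of European outpatient HFrEF, patients may look younger and less comorbid than they are. The narrow intervals planned in Section 7.5 would not reveal this, because a gap in the frame does not shrink as the sample grows.

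**Working it through.** **Step 1: does any design measure cover physician type?** The measures offered for representativeness are:
- allocation of patient numbers to countries or country clusters (Section 7.2.1);
- consecutive enrolment (Sections 7.2.1 and 7.9);
- few eligibility restrictions (Section 7.2.3);
- no mandated diagnostic or therapeutic procedures (Section 7.9).

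The first balances countries. The others act within the sites already chosen. None concerns which kinds of physician are sampled. Section 7.9 discusses selection by the investigator and the two-wave SoC enrolment, but not the specialist-only frame.

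**Step 2: reproduce the plan's precision.** The half-width for a proportion at its widest (p = 0.5) is 1.96 × √(0.25/n).
- n = 6000: 1.96 × √(0.25/6000) = 1.27 points; the plan says ±1.3.
- n = 3000: 1.96 × √(0.25/3000) = 1.79 points; the plan says ±1.8.

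Both figures reproduce. They describe sampling error around the mean of the sampled frame and nothing else.

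**Step 3: what a frame gap would add.** Let w be the share of the claimed population outside the frame, and d the difference in a characteristic between patients outside and inside it. The claimed population's value is (1 − w) × inside + w × outside, while the study estimates the inside value. The bias is therefore w × d in size, whatever n is.

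The documents give neither w nor d. All values below are assumptions, chosen to show a range. Coverage is the chance that the nominal 95% interval at n = 6000 contains the value for the claimed population (normal approximation, p = 0.5, standard error 0.645 points).

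| Assumed w | Assumed d (points) | Bias (points) | Bias ÷ 1.27 | Coverage |
|---|---|---|---|---|
| 10% | 5 | 0.5 | 0.4 | 88% |
| 20% | 10 | 2.0 | 1.6 | 13% |
| 50% | 10 | 5.0 | 4.0 | about 0% |

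The bias equals the stated half-width when w × d = 1.3 points, for example w = 26% with d = 5, or w = 13% with d = 10. It can thus lie well inside or well outside the interval, and the documents do not settle which.

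**The case against.** The strongest reply is that nothing is hidden. The specialist setting is stated in the abstract and in Section 7.2.1, the wide objective in Section 6 is an additional one, and *overall* there could mean the two cohorts combined. That stands as far as it goes: this is over-claiming, not concealment. It does not explain the references to the outpatient sector in Europe in Section 6 or to the outpatient sector in Section 7.9, which remain broader than the frame.

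Several stronger readings are tempting, and the documents do not support them.

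- *That the protocol blames non-expert GP care for misleading data.* The sentence in Section 5 is one of several explanations for poor prognosis. The criticism of existing registries, in Sections 2 and 5, is aimed mainly at tertiary and hospital recruitment and at mixing acute with chronic HF. Office-based recruitment answers much of that.
- *That drug use or dose reached is known to differ by provider.* Section 5 describes adherence to treatment recommendations in primary care as insufficient in much the same way as in tertiary centres, and says office-based cardiologists have hardly been studied on this. The text supports a provider difference for age and comorbidity only.
- *That most HFrEF patients are outside the frame.* The sentence concerns CHF, which includes HFpEF, and gives no percentage. Section 5 also says the recommended work-up seems to reach only a fraction of primary care patients, so an unknown share of those patients might lack the imaging evidence of reduced LVEF that Section 7.2.2 requires.
- *That Section 7.2.3 contradicts the frame.* Its phrase "representative of) the real population of CHF patients with reduced LVEF managed in the office-based setting" is hedged, is limited to office-based care, and explains why there are few patient-level criteria. It is weak evidence either way.

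**Conclusion.** The protocol states a property that its design does not have. It claims the overall outpatient HFrEF population, and a representative picture or sample, from a frame confined to cardiologists and HF-specialist primary care physicians. Its own background gives reason to expect that the excluded sector differs in age and comorbidity. Neither the design nor the limitations section deals with this.

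The consequence is limited. The stated precision is correct for what it measures, and describing profiles within specialist office-based care remains sound. What fails is the extension to the whole outpatient sector. A reader might infer a definite bias of several points, but the documents do not support that. The illustrative 0.5 to 5.0 points rest wholly on assumed shares and differences. They show only that the bias could be smaller or larger than ±1.3 points and that sample size does not reduce it.

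This cannot be left to the analysis plan. Target population, frame and limitations are fixed in the protocol, and no later analysis can supply patients who were never eligible to be sampled.

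**What to change.** 1. In Sections 2, 6, 7.7 and 7.9, restate the target population as HFrEF patients managed by office-based cardiologists and HF-specialist primary care physicians, and qualify *overall* and *representative* accordingly.
2. In Section 7.9, name the non-specialist general practitioner sector as not sampled. Say that age and comorbidity burden may differ there, and that the intervals in Section 7.5 do not cover this.
3. Show the main baseline tables by provider type (cardiologist or primary care physician). The protocol does not say that provider type is recorded; if it is not already held, record it once per site. State that this split compares two kinds of specialist provider and says nothing direct about the excluded general practitioners.

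The cost is wording, one site-level attribute and one more stratifier. No patient, visit or treatment changes. The downside is a narrower stated scope.
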